An individual patient will be involved in the study for a total of up to 3 months. They will complete a screener enrollment interview, a T1 in person or phone interview as soon as possible following the screener, and a final T2 interview on the phone at 3 months.

[figure not shown]
We anticipate that patient enrollment will actively take place until Q2, 2020.

Our proposed/anticipated study timeline is below.

Table 4 shows study measures and outcomes.

			Inter	view			
Variable	Instrument(s) or Measure(s)		T1			T2	EHR Reviev
Covariates		_					
Socio-demographics	Age, sex, race/ethnicity, education, income, insurance/work status, living situation	Summary	•				
Baseline Health Status	Self-reported overall health/chronic conditions	ung	•				
Health Literacy	Chew		•				
Social Support	Tangible social support scale, marital status	Med	•	Week	month		
Patient Activation	Consumer Health Activation Index (CHAI)		•	Ve.	0		
Effectiveness Outcomes		and		7	Е		
Medication Knowledge	Dosage, storage, indication, risks and benefits, side-effects		•		Ξ	•	
Medication Adherence	Self report fill and time to fill	ing	•	ij	ire	•	
	Proper use	sel	•	Ĕ	na	•	
	ASK-12	Ë	•	ō	ou	•	
Fidelity Outcomes		counseling,		Questionnaire-	Questionnaire		
Provider Counseling	Receipt of provider counseling (yes/no)		•	ne	ne		
Qualify of Provider Counseling	CAHPS- communication about medicines	RX	•	g			
Receipt of Materials	Receipt of Med Guide (yes/no)	Ă,	•	rta	tal		
Perceived Helpfulness	How helpful was intervention? (1 to 10 scale)	BPA,	•	Portal	Portal		
Pharmacy Counseling	Receipt of pharmacy counseling (yes/no)		•	-	а.	•*	
Qualify of Pharmacy Counseling	CAHPS- communication about medicines	Visit-	•	1		•*	
Receipt of Portal Email	Completion of portal assessment (yes/no)					•	
	How helpful was intervention? (1 to 10 scale)	Clinic				•	
Clinic Staff Follow-Up Counseling	Receipt of counseling (yes/no)	C				•	
Quality of Clinic Staff Counseling	Self-reported clinic follow-up					•	
Frequency of Clinic Follow-Up	EHR Review of clinic contact with patient			1			•

Figure.1 Illustrates the study design

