9.1. Effectiveness Assessments

9.1.1. Primary Effectiveness Assessments

Medication Knowledge. Medication-specific knowledge measures will be created to determine whether a patient has a basic understanding of their prescribed medication. This will comprise a set of objective, open-ended, yet targeted questions with predetermined correct responses known for each medication under study. Patients will be asked about their medication's 1) indication, 2) risks or warnings (knowledge of at risk/warnings, correct or incorrect per warning), and 3) side effects (knowledge of at least two side effects, correct or incorrect per item). Correct answers will be tailored to the available content included in the MedGuide Summary, as done previously by our team.(11-14) While patients are not given response options to facilitate their answer, interviewers will both document the verbatim response to each question and code it as correct or incorrect. A second, independent reviewer, blinded to the research interviewer's code of correct/incorrect, will rate the responses. Any discordance will be resolved through team discussions. Total scores will range from 0-100, calculated reflecting the percent correct of possible points.

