10.1. Sample Size Determination

The sample size for this pragmatic study was based on comparisons of the primary outcome of medication knowledge between the two arms (i.e., usual care vs EMC²) at the T2 interview. We expect patients in the usual care arm to score an average of 55.6% correct responses (SD=28.4) based on a previous study that tested comprehension of the FDA standard Med Guides to those to be used in this study(9). Enrolling 330 patients and estimating 90% retention at the T2 interview (N=300, 150 per arm, 6 per provider), we will have 80% power to detect a minimum difference of 9.4% between the EMC² and the usual care arm assuming a Type I error of 5% (improving from 55.6% to 65.0% or greater). An intra-class correlation coefficient (ICC) of 0.001 was used; we expect clustering of physicians to have minimal influence on outcomes. However, even if the ICC were higher (i.e. 0.01) we could still detect a difference as small as 9.6%.

With the sample size set by the primary outcome, we also report minimum detectable differences for medication adherence measures. We estimate 65% of the usual care arm to demonstrate proper use of their medications based on prior studies(1, 18). With similar assumptions described above, a sample of 300 participants would enable us to detect a minimum absolute difference of 14.4% between arms with an ICC of 0.001 and 14.7% with an ICC of 0.01. We expect participants in the usual care arm to score an average of 27.5 (SD=7.2) on the ASK-12 based on validation studies(15). Retaining 300 participants (150 per arm, 6 per provider) at the T2 follow-up interview we will have 80% power to detect a minimum difference of 2.4 between the EMC² and the usual care arm (improving from 27.5 to 25.1 or less) using an ICC of 0.001 and a difference of 2.5 (improving from 27.5 to 25.0 or less) and with an ICC of 0.10. While no cut-off indicating non-adherence is provided, the goal would be for patients to score below 22.5, the average score in patients who took medications exactly as directed in the ASK-12 validation studies(15). We could detect differences smaller than this with the proposed sample size. In addition, differences in subscale scores of 1.3 for behavior, 0.9 for health beliefs, and 1.0 for inconvenience/forgetfulness could be detected between arms assuming mean scores of 10.5 (SD=3.8), 8.1 (SD=2.7), and 8.9 (SD=3.0), respectively, in the usual care arm.

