10.3.3.3. Tertiary/Exploratory Analyses

Aim 3. Evaluate the fidelity of the EMC² Strategy to promote provider counseling, deliver patient Rx information, and inform providers of potential harms.

Compared to usual care, patients receiving the EMC² strategy will:

- 1) report higher rates and quality of provider Rx counseling
- 2) report higher rates of receipt of print Rx information

Appropriate bivariate analyses will be performed based on each outcome measure described below using t-tests, Wilcoxon Rank-Sum, or $\chi 2$ tests, as appropriate.

Provider Rx Counseling. We will ask patients (yes/no) whether their provider(s) (physician/nurse) counseled them on their prescribed medication. We will also ask adapted questions from the Health Literacy supplemental items of the Consumer Assessment of Health Providers Survey (CAHPS) to evaluate the extent and quality of physician verbal counseling.

Receipt of print Rx information. All patients will be asked whether they received any print Rx information at their appointment. We will further probe intervention patients to determine whether the health literate Med Guide Summary was specifically received and its perceived helpfulness. Additionally, we will also collect EHR data to determine whether the Med Guide Summary was printed with their after-visit summaries.

We will also examine completion rates of:

- 1) the EHR portal survey by patients in the intervention arm
- 2) clinic follow-up for patients identifying Rx concerns in the portal survey.

Completion of the EHR Portal Survey. Intervention patients will be asked (yes/no) whether they received the emails to visit the portal and if they completed the portal questionnaire. We will also confirm this by determining if portal questionnaire results were populated in the EHR.

Clinic follow-up for patients identifying Rx concerns. At each performance site, clinical liaisons will share with the study team what specific medication-related concerns that are self-reported by patients via the portal assessment might warrant follow-up. It is at the discretion of each clinical practice to choose how they will triage the information provided via the feedback from the EMC2 intervention, and as part of the study we will explore the frequency and nature of follow-up that occurred for various medication-related concerns by self-report and in the EHR.

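### The plan does not state that the people who code and adjudicate the open-ended answers behind the primary knowledge score are masked to arm

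*Combined protocol and SAP*

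**What the plan says.** Section 10.1 sizes the trial on "comparisons of the primary outcome of medication knowledge between the two arms" at T2. Section 9.1.1 describes how the score is made. Questions are open-ended, "with predetermined correct responses known for each medication under study", and there are three human steps:

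1. **First coding.** The "interviewers will both document the verbatim response to each question and code it as correct or incorrect".
2. **Second rating.** The sentence that opens "A second, independent reviewer, blinded to the research" goes on to name the interviewer's correct/incorrect code as the thing concealed. Arm is not mentioned.
3. **Adjudication.** "Any discordance will be resolved through team discussions".

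Section 7.4 (Blinding) calls the study open-label and says researchers cannot be fully blinded. It makes no exception for outcome coders. Section 10.3.3.3 says intervention patients will be asked "whether they received the emails to visit the portal and if they completed the portal questionnaire". Table 4 in Section 5.1, whose layout is damaged in the copy reviewed, appears to place the portal items and the clinic follow-up items at T2. Section 5.1 also says Northwestern research assistants collect all the data. Nothing in Section 10 adds masked coding.

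**The concern.** Blinding the second reviewer to the first code keeps the two ratings independent of each other. It does not keep either rating independent of treatment arm. If both raters know the arm they can lean the same way, and double rating does not remove a shared lean.

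The plan provides for discordance, so it expects some judgement calls. Those are the answers where knowledge of arm could matter most, and they go to the least structured step, a discussion with no stated masking. The outcome affected is the primary one. If the result is positive, a critic can ask whether borderline answers were credited more readily in the intervention arm, and the protocol as written gives no reply.

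**Working it through.** **Can the coders know the arm?** Setting the sections side by side:

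| Step (Section 9.1.1) | Concealment stated | Route to knowing the arm |
|---|---|---|
| Interviewer codes | None | Open-label (7.4); portal questions for intervention patients (10.3.3.3), apparently at T2 (Table 4) |
| Second reviewer rates | Interviewer's code only | Not stated; nothing separates this person from arm, prescriber or portal data |
| Team settles discordance | None | Not stated; the team may include the interviewer |

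Two limits apply. The order of items within T2 is not given, so the knowledge items may already come before the portal items. The item "Receipt of Med Guide (yes/no" in Table 4 appears to be asked at T1, and Section 7.1 allows variable distribution of Medication Guides under usual care. That item alone therefore does not reveal arm. The portal items and the extra Summary probe in Section 10.3.3.3 do.

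**What would a given shift do?** The documents contain no figure for miscoding, so the shift is an assumption.

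Inputs: SD 28.4, 150 per arm, 6 per provider, ICC 0.001 with 0.01 as the alternative (Section 10.1); two-sided alpha 0.05 (Section 10.3.1); about 50 prescribers (Section 7.3), giving 50 − 2 = 48 degrees of freedom.

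Standard error of the difference between arms:

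SE = 28.4 × √[(2/150) × (1 + 5 × 0.001)] = 3.29

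With ICC 0.01 the SE is 3.36.

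*Check against the plan.* With a noncentral t on 48 df, the difference detectable with 80% power is 9.40 points at ICC 0.001 and 9.61 at ICC 0.01. Section 10.1 states 9.4 and 9.6, so the model reproduces the plan's own figures.

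*Rejection rate with no true effect.* For an assumed net shift b in the final score in favour of the intervention, the noncentrality is b/SE. The rejection rate is the sum of the two tails:

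| Shift b (points) | Share of 9.4 | Upper tail | Lower tail | Total, ICC 0.001 | Total, ICC 0.01 |
|---|---|---|---|---|---|
| 1 | 10.6% | 4.83% | 1.20% | 6.02% | 5.98% |
| 2 | 21.3% | 8.63% | 0.53% | 9.16% | 8.98% |
| 3 | 31.9% | 14.33% | 0.22% | 14.55% | 14.13% |

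(Totals are from unrounded tails.) A shift of 1 point means that a net 1 in 100 of possible points is coded differently because of arm and stays so in the final score.

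**The case against.** The plan is silent on arm masking; it does not say that the second reviewer is unmasked. That reviewer is described as independent and rates the recorded answers, and nothing says they see arm. Section 7.4 discloses that blinding is incomplete. The coding matches targeted questions to a fixed key, item by item, so bias must either be shared by both raters or enter when disputes are settled. If it enters only through adjudication and 10% of items are discordant (an assumption), a 3-point shift needs a difference of 3/10 = 30 percentage points between arms in how disputes are settled. The 3-point case is therefore demanding, and at 1 point the effect is small. The evidence that arm is revealed also concerns the interviewer more than the second reviewer.

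Much of this stands. It shows that the bias may well be small, and that the shift figures illustrate the risk without measuring it. It does not supply the missing safeguard. Section 9.1.1 says exactly what the reviewer is blinded to, and arm is not included. Section 7.4 may explain why interviewers are unmasked, but it gives no reason to leave unmasked a reviewer or adjudicators who can work from text alone.

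**Conclusion.** The concern holds. For the T2 primary score, no section states that the interviewer, the second reviewer or the discordance discussion is masked to arm, and the trial is open-label with questions that reveal arm in the interview. This rests on the text and does not depend on the calculation.

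The size of the bias is unknown. On assumed net shifts of 1 to 3 points, the false-positive rate rises from 5% to between about 6.0% and 14.5% (about 14.1% at the upper end with ICC 0.01). The planned safeguards make the larger shifts less likely. This is an avoidable weakness in the primary endpoint that should be corrected; it is not a fatal flaw. The power calculation is not affected.

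**What to change.** Amend Section 9.1.1, with a matching sentence in Section 7.4:

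1. Export the verbatim T2 knowledge answers with study ID and drug only, leaving out arm, prescriber and fidelity items. In this export copy, redact any mention of the sheet or the portal. The source record stays intact.
2. Have the planned second reviewer, and the discordance resolution, work from that file masked to arm. Use team members who did not interview those patients, and do not show adjudicators who gave which code.
3. State that this masked, adjudicated code is the one used in the primary analysis.
4. At T2, ask the knowledge items before any portal or clinic follow-up item.

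The answer key based on the Summary is a disclosed design choice and is left as it is.

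The cost is protocol wording, one export step with a check of the free text, and allocation of tasks within the team. Appendix 3.2.1 already has survey data downloaded periodically from REDCap under a study ID. Team size is not given, so separating interviewers from adjudicators needs to be confirmed as workable. Section 3.3 gives Northwestern study personnel access to the file linking IDs to patients, so those rating and adjudicating should not consult it. No visit, question or sample size change is needed, and the planning values of 55.6 (SD 28.4) stand.

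One risk remains: an interviewer who knows the arm still elicits and records the answers. Item order reduces that risk but does not remove it.

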9.1.2. Secondary Effectiveness Assessments

Medication Adherence. Medication adherence refers to a patient's medication taking behavior in terms of the extent to which he or she takes the medication as prescribed. We will assess medication adherence by 1) treatment initiation (yes or no), 2) time to fill (# of days from prescription order to patient fill), 3) subjective self-report of medication adherence behaviors (ASK-12), 4) objective assessment of proper use.

- 1) *Treatment initiation*. Patients will be asked whether they have filled their study prescription (yes or no), and whether they intend to fill it.
- 2) *Time to fill.* We will calculate the number of days between the date the medication was ordered and when the medication was actually filled, based on the patient's self-report of the date of fill stated on the medication's prescription label from the pharmacy.
- 3) ASK-12. The ASK-12 survey is a widely used and previously validated psychometric measure of adherence that covers three domains: inconvenience/forgetfulness, treatment beliefs and behavior(15). In a study among 112 adults with asthma, type II diabetes or congestive heart failure, the tool demonstrated good internal consistency reliability (Cronbach's α 0.75) and test-retest reliability (intraclass correlation 0.79); convergent validity was also demonstrated through correlations with multiple other measures (16, 17) and pharmacy claims data (15). Ask-12 scores range from 12-60, with higher scores translating to greater barriers to adherence.
- 4) Proper use. For the study medication, patients will be asked on what day they last took the medication. While most medications will be daily and the correct response would be 'yesterday' or 'today', some prescribed drugs of interest may be taken weekly or in another manner as directed by their physician. Patients will then be asked 1) How many times during the day did you take it? 2) At what hour/s of the day did you take this medicine? and 3) How much of this medicine did you take each time? A patient's proper timing (last day and # of times per day), dosing (number of pills per dose), and spacing between doses (for BID, TID medications only) will be coded as correct or incorrect. Patients will be classified as having properly used their medication if they correctly reported all components.

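### Proper use accepts a last dose taken today and then scores that day's dose count and spacing, so an adherent BID or TID patient interviewed mid-day is coded as an improper user

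*Combined protocol and SAP*

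**What the plan says.** Section 9.1.2 (Proper use) first asks on what day the study medicine was last taken: "While most medications will be daily and the correct response would be 'yesterday' or 'today". Weekly and other schedules are acknowledged separately. The patient is then asked "How many times during the day did you take it", at what hours, and how much each time.

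Two of the scored components apply to every regimen: "A patient's proper timing (last day and # of times per day), dosing (number of pills per dose". A third is reserved for regimens with several doses a day: "spacing between doses (for BID, TID medications only) will be coded as correct or incorrect". The classification is all-or-none: "Patients will be classified as having properly used their medication if they correctly reported all components".

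Proper use is one of four adherence measures under the secondary objective. Table 4 collects it at T1 and T2, and section 10.3.3.2 analyses it as a binary outcome with a logit link. Section 10.1 plans on "We estimate 65% of the usual care arm to demonstrate proper use of their medications", citing prior studies, and says that 300 participants suffice to "detect a minimum absolute difference of 14.4% between arms with an ICC of 0.001 and 14.7% with an ICC of 0.01". The same section states that the sample size was set by the primary outcome, medication knowledge.

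**The concern.** When the patient truthfully answers that the last dose was today, the only day named so far is one that has not ended. A BID patient called at 10:00 who took the morning dose at 8:00 answers: today, once, 8 am. Against a twice-daily regimen the count is wrong, and with one recorded hour there is no spacing to score. One failed component is enough, so the patient is coded as an improper user. Interviewed at 21:00, after the second dose, the same patient passes.

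Part of the result therefore reflects when the interview took place rather than how the medicine was taken. False negatives of this kind, equally frequent in both arms, lower both proper-use rates by the same factor and so shrink the difference between them. What is at stake is the sensitivity of one secondary endpoint and the meaning of its reported rates.

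**Working it through.** **1. Does any text prevent the miscoding?** Section 9.1.2 does not define the day that the count refers to, send the interviewer to the last full day, or excuse doses not yet due. The schedule in section 2 and section 7.9.4 set interview dates, not hours. Section 10.3.3.2 takes order dates and the sig from the EHR, but gives no rule for using them to excuse a dose that is still to come.

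**2. Inputs from the documents.** Usual care 65%, 150 per arm, 6 per provider, ICC 0.001 or 0.01 and 80% power (section 10.1); two-sided alpha 0.05 (section 10.3.1).

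**3. Reproducing the plan's figure.** Effective n per arm = 150/[1 + (6 − 1) × ICC], which is 150/1.005 = 149.25 at ICC 0.001 and 150/1.05 = 142.86 at ICC 0.01.

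Power = Φ{[d√n − 1.96√(2p̄(1 − p̄))] / √(p₁(1 − p₁) + p₂(1 − p₂))}, where d = p₂ − p₁ and p̄ is the mean of the two rates.

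For 65.0% v 79.4% at ICC 0.001: d√n = 0.144 × 12.217 = 1.759, so the argument is (1.759 − 1.96 × 0.6336)/0.6254 = 0.827 and power is 79.6%. The minimum detectable difference is 14.5 points at ICC 0.001 and 14.8 at ICC 0.01, against the stated 14.4 and 14.7. The plan's figures reproduce.

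**4. Dilution.** Let f be the share on BID or TID drugs and q the share of those who answer today before their last dose. Neither is in the documents. With equal false negatives in both arms and no false positives, coded rate = s × true rate, where s = 1 − f × q. The coded difference is then s × the true difference.

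Taking 65.0% and 79.4% as true rates, ICC 0.001:

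| Affected share (assumed f × q) | Coded rates | Difference, points | Power | True difference needed for 80% power, points |
|---|---|---|---|---|
| 0% | 65.0% v 79.4% | 14.4 | 80% | 14.5 |
| 2.5% (10% × 25%) | 63.4% v 77.4% | 14.0 | 76% | 15.1 |
| 5% (20% × 25%) | 61.8% v 75.4% | 13.7 | 72% | 15.7 |
| 10% (20% × 50%) | 58.5% v 71.5% | 13.0 | 65% | 17.0 |
| 20% (40% × 50%) | 52.0% v 63.5% | 11.5 | 52% | 19.8 |

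The unpooled-variance formula moves these powers by about one point or less (53% in the last row).

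**5. If the 65% is already on the coded scale.** The 14.4-point figure then stands for the coded rates, and the true difference behind it is 14.4/s. At 10% affected this is 14.4/0.90 = 16.0 points (true rates 65/0.90 = 72.2% and 79.4/0.90 = 88.2%).

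**The case against.** The strongest reply is that section 9.1.2 summarises the measure. The interview script and coding guide are not in the documents, and the day in the count question is undefined, so it could mean a full or typical dosing day. A coder who sees one dose at 8 am against a twice-daily sig might also recognise that the second was not yet due. This stands as a limit: practice may be better than the text. It does not remove the point, because the text accepts today, counts doses next, and contains no rule that would lead two coders to the same answer.

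The reply on size also stands. Only patients on BID or TID drugs who answer today mid-day are affected; once-daily and weekly users are not. Many of the targeted drugs are injectables (section 9.1.3), and metformin is capped at 50 patients per site (section 6.2). The affected share is unknown, and one shrink factor assumes similar proper use and similar effect across regimens.

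Three stronger readings are tempting but unsupported:

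- **That the 65% rate and the 14.4-point difference no longer apply.** The 65% comes from prior studies whose question format is not shown, so it may already be on the coded scale.
- **That the trial loses the power it was sized for.** The knowledge outcome set the sample size; proper use has only a reported detectable difference.
- **That the comparison is biased between arms.** That would need interview hours to differ by arm. Section 5.1 has the same institution's assistants collecting all data, and section 2 gives one interview schedule without distinction by arm.

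**Conclusion.** The point holds as a defect in the scoring rule of one secondary endpoint. Followed as written, section 9.1.2 codes an adherent BID or TID patient as an improper user if the interview falls between the first and last dose of the day. If this happens equally in both arms, the coded difference shrinks in proportion to the affected share.

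The direction follows from the text; the size rests on assumption. At 2.5% to 20% affected, and with 65.0% and 79.4% as true rates, power goes from about 80% to between about 76% and 52%. If the planning rate already contains the miscoding, the stated detectable difference is correct on its own scale but understates the true difference required. The primary endpoint and the sample size are untouched.

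**What to change.** In section 9.1.2, keep the item on the last day taken and its scoring. Ask the count, hours and amount about the last complete dosing day: yesterday for daily drugs, even if a dose has already been taken today, and the last scheduled dosing day otherwise. Score number of times, amount and spacing on that day only. If the interview script already does this, write the rule into 9.1.2.

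The cost is one line in the script and one in the scoring rule, with slightly longer recall for patients who would otherwise have described today. No extra patients, staff or visits are needed.
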